### 5.6 Missing values

Missing STT values for a time point will be treated as missing. When STT detection takes longer than 1 hour, the STT will be considered as 1 hour. When the subject is not able to test saccharine on direct application, the STT values should be treated as missing, and these subjects should not be included in the STT analysis.

Regarding plasma nicotine samples:

- Missing sampling time: if the time of collection for a sample is unknown, that individual data point will be treated as missing data for descriptive statistics.
- Missing concentration data: missing concentration data will be treated as missing and replaced with a "." in the concentration dataset. No values will be imputed.
- Concentration data below lower limit of quantification (LLOQ=0.399 ng/mL): in the calculation
  of descriptive statistics for concentration data at each sampling time point, all LLOQ values will
  be treated as zero for time zero and as 1/2 LLOQ for the remaining time

### 6 CLARIFICATIONS TO THE STUDY PROTOCOL

In the study protocol, the populations that should be considered in each statistical analysis is not clear. In this SAP the following assumptions were considered:

- Statistical analysis for demographics will be performed for the FAS and PP population;
- Primary analysis will be performed for the FAS and PP population;
- Safety analysis will be performed for the safety population.

### 7 APPENDIX 1: DERIVED VARIABLES

The following variables will be derived:

Group of subjects – A dichotomous variable (smoker/never smoke) will be calculated.

Smoker – subjects who meet all of the following criteria at Visit 1 and at Visit 2:

- A positive urine cotinine test (=200 ng/mL).
- Smoked at least 20 cigarettes per day for at least the past 5 years.
- eCO levels >10 parts per million (ppm).
- No plans to quit smoking in the next 3 months.

Never smoker – subjects who meet all of the following criteria at Visit 1 and at Visit 2:

- Subject who has smoked less than 100 cigarettes throughout their lifetime and no cigarettes in the past 3 years.
- A negative urine cotinine test (<50 ng/mL).
- eCO levels = 5 ppm.

**STT** – At each time point, STT value will be obtained as the difference between end time and start time, in minutes, of STT test. When STT detection takes longer than 1 hour, the STT will be considered as 1 hour (60 minutes). When the subject is not able to test saccharine on direct application, the STT values should be treated as missing, and these subjects should not be included in the STT analysis.

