# 5.4 Violation of Selection Criteria

Study participants who are eligible at Screening (Visit 1), but who do not meet the entry criteria at Visit 2, will be considered as a screen failure until enrollment is completed.

If a violation of selection criteria after enrollment is detected, the study participant may be discontinued from the study at the discretion of the Principal Investigator or designee. If study participants are not yet enrolled, they can be replaced. If study participants are enrolled, and the Principal Investigator decides that they should be discontinued from the study, they will not be replaced.

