### 5.3 Analysis datasets

#### 5.3.1 Full Analysis Set (FAS)

All study participants who have at least one evaluable STT test at Visit 3 will be included in FAS population.

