#### 5.3.2 Per Protocol (PP) Population

All study participants in Full Analysis Set who have no major protocol deviation will be included in the PP population.

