### 5.3.3 Safety Population

All enrolled subjects will be included in safety population.

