#### 5.5 Statistical analysis

All quantitative variables will be summarized through descriptive statistics namely mean, median, standard deviation, quartiles (Q1 and Q3) and minimum and maximum values. Qualitative variables will be summarized through number (n) and frequency distribution (%).

All descriptive analyses will be performed by smoker and never smoker group.

Statistical tests will be two-tailed considering a significance level of 5%.

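### The SAP derives smoking group from the inclusion-5 items at both visits, so an enrolled man who turns out to fail one of them has no column in the by-group FAS and Safety tables

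*SAP*

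**What the plan says.** **Group.** SAP Appendix 1 says of the group variable: "A dichotomous variable (smoker/never smoke) will be calculated". The two levels are "Smoker – subjects who meet all of the following criteria at Visit 1 and at Visit 2" and "Never smoker – subjects who meet all of the following criteria at Visit 1 and at Visit 2". The items listed under each are those of inclusion criterion 5: cotinine, cigarettes per day, eCO and no plan to quit for smokers; lifetime and recent cigarette use, cotinine and eCO for never smokers. There is no third level and no rule for a man who meets neither definition.

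**Analysis sets.** Safety (SAP 5.3.3): "All enrolled subjects will be included in safety population". FAS (SAP 5.3.1): "All study participants who have at least one evaluable STT test at Visit 3 will be included in FAS population". PP (SAP 5.3.2): "All study participants in Full Analysis Set who have no major protocol deviation will be included in the PP population".

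**Violators.** Protocol 5.4 leaves it to the site whether such a man goes or stays: "If a violation of selection criteria after enrollment is detected, the study participant may be discontinued from the study at the discretion of the Principal" (quotation cut short here). Enrolled men are not replaced. Protocol 11.1.2 counts a breach of an inclusion or exclusion criterion as a protocol deviation.

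**Presentation.** SAP 5.5: "All descriptive analyses will be performed by smoker and never smoker group". In the shells, Tables A 2 to A 8 and A 10 to A 16 have smoker and never-smoker columns only. Table A 1 adds a total column, and Table A 9 has a total column alone.

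**Cotinine.** For never smokers, Appendix 1 requires a value below 50 ng/mL. SAP 4.1 and protocol 5.1.1 require a value below 200 ng/mL.

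**The concern.** Membership of the analysis sets and membership of a group rest on different rules. The first has no eligibility condition for Safety or the FAS, while the second is an eligibility test. A man can therefore belong to a set and to neither of the two columns in which that set is tabulated.

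The plan already has a place for selection violations: they are deviations, and the PP set removes the major ones. Putting inclusion criterion 5 into the group variable applies a PP-type exclusion a second time, to tables labelled FAS and Safety. For that criterion, comparing FAS with PP results would then show nothing. An adverse event in such a man would be absent from the counts and the denominators of Tables A 11 and A 12, although he is in the Safety set.

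With 7 men per group, one unclassified man is a noticeable share of the data. What to do with him would have to be settled after the data are seen, and SAP section 1 gives prospective definition as a purpose of the document.

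**Working it through.** **1. Follow three enrolled men through the definitions.**

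| | Fails an inclusion-5 item, found after enrolment | Eligible never smoker, cotinine 50–199 ng/mL | Fails another criterion (e.g. BMI, medication) |
|---|---|---|---|
| Safety | in | in | in |
| FAS | in, if one evaluable Visit 3 STT | in, if one evaluable Visit 3 STT | in, if one evaluable Visit 3 STT |
| PP | out if the deviation is major | no deviation on this ground | out if the deviation is major |
| Derived group | neither | neither | smoker or never smoker |
| Tables A 2–A 8, A 10–A 16 | no column | no column | tabulated as his sets allow |
| Table A 1 total, subject listings | shown | shown | shown |
| Table A 9 (FAS, total only) | shown if in FAS | shown if in FAS | shown if in FAS |

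The first man is in Safety even if the investigator discontinues him, because that set needs only enrolment. With one such man among 14, Table A 1 would show a total of 14 against 13 in the two groups.

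The second man has broken no criterion. His case assumes that cotinine is recorded as a number, which the documents do not state. Appendix 1 also prints equals signs at 200 ng/mL and 5 ppm; these may be inequality signs lost in reading the PDF, and nothing here rests on them.

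**2. The plan's own figure.** Inputs from SAP 5.1 and 5.5: 7 per group, SD 2.5 min, two-sided 5%. Power is not stated; 80% is assumed. By the normal approximation:

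(1.960 + 0.842) × 2.5 × √(1/7 + 1/7) = 3.74 min

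This reproduces the stated 3.75 min.

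**3. One man unclassified (6 against 7), same formula.**

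(1.960 + 0.842) × 2.5 × √(1/6 + 1/7) = 3.90 min

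**4. 95% CI for one group's mean STT.** The plan tests no hypothesis on STT, so this is the more relevant measure. Half-width = t(0.975, n−1) × SD / √n.

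- n = 7: 0.925 SD, or 2.31 min at SD 2.5.
- n = 6: 1.049 SD, or 2.62 min at SD 2.5.
- Ratio: 1.049 / 0.925 = 1.13, about 13% wider.
- At SD 6, as reported for smokers in the study cited in protocol 2.1: 5.55 and 6.30 min.

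**5. Adverse events.** If the unclassified man has one and nobody else in his group does, the as-enrolled rate is 1/7 (14%). Under the derivation it is 0/6.

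Steps 3 to 5 are illustrations with one man. The documents give no violation rate and no distribution of cotinine in never smokers.

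**The case against.** The items in Appendix 1 are themselves the entry test. Cotinine, eCO and smoking history are checked at Visit 1 and again at Visit 2, where enrolment takes place, and under protocol 5.4 a man who fails at Visit 2 is a screen failure. Derived group and enrolled group should then agree. Disagreement on a true violation needs a missed or misrecorded check. A plan to quit first formed after Visit 2 would not count. Calling the variable dichotomous suggests that the authors took every participant to be one or the other, and a programmer might simply use the enrolled group. The study is exploratory, and a somewhat wider descriptive interval changes no decision.

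Much of this stands. The trigger is uncommon, and that keeps the severity low. It does not remove the problem, because Appendix 1 states a rule and that rule gives no answer for such a man. The cotinine mismatch also needs no missed check at all.

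Four stronger readings might be inferred, and the documents do not support them:

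- That any selection violator drops out. Only the inclusion-5 items are repeated in Appendix 1; violators of other criteria keep their group, so FAS and PP can still differ for them.
- That the FAS is defined by enrolment. Only Safety is; the FAS depends on an evaluable Visit 3 STT.
- That the SAP excludes these men. It has no such sentence; their absence follows from reading the definitions together.
- That their adverse events are lost from the report. Listing 13 gives every event by subject, Listing 14 the serious ones and Listing 2 the deviations. What is affected is the summary tables.

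**Conclusion.** The point holds in a limited form. Taken literally, the Appendix 1 rule leaves two kinds of enrolled men without a column in Tables A 2 to A 8 and A 10 to A 16: one who fails an inclusion-5 item, and a fully eligible never smoker with cotinine of 50–199 ng/mL. Both are in Safety, and in the FAS with one evaluable Visit 3 STT.

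For one man, the effect is 1 of 7 (14%) of a group and an interval for the group mean about 13% wider. This assumes that the derivation is programmed as written. How many men would be affected cannot be learned from the documents, and it may be none. Aligning the cotinine cut-offs would deal with the second kind of man but not the first.

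Low severity: a clarification worth making because it costs almost nothing, not a threat to the study's conclusions.

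**What to change.** In SAP Appendix 1:

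1. Define Group as the group in which the participant was enrolled (Group 1 or Group 2, protocol section 5), and use it for all FAS and Safety tables.
2. Record failure of an inclusion-5 item as a protocol deviation, and handle it through the PP set under that set's major-deviation rule.
3. Reconcile the 50 ng/mL cut-off in Appendix 1 with the 200 ng/mL in SAP 4.1 and protocol 5.1.1.

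The cost is a sentence or two in the SAP and one corrected figure. No new data are needed, because the group is known at enrolment.

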# **4** INVESTIGATIONAL PLAN

# 4.1 Overall Study Design and Plan

This will be a single-center study in which 14 healthy adult male study participants, consisting of 7 cigarette smokers and 7 never smokers as a control group, will be enrolled. Study participants will not be replaced after being enrolled.

This study will have three visits on three separate days as described in Figure 1.

At Visit 1 (Screening Visit), study participants will undergo the procedures outlined in Appendix A to check eligibility criteria, including providing informed consent, undergoing a brief physical examination (including an examination of the head and neck, chest, heart (cardiovascular) and abdomen), nasal and throat exam, vital signs, skin prick test (SPT), spirometry testing, STT test, exhaled carbon monoxide (eCO) measurements, urine cotinine assessment, medical and smoking history and blood and urine collection for medical lab exams.

Following Visit 1, study participants who pass all of the inclusion criteria and do not present any of the exclusion criteria will be asked to return to the clinic for Visit 2.

During Visit 2, selected inclusion and exclusion criteria will be reassessed to ensure study participants are still eligible for enrollment (Appendix A). All study participants will have baseline assessments performed (Appendix A), including STT test.

Study participants will be confined in the clinic from the beginning of Visit 2 until discharge at Visit 3. During this confinement period study participants will abstain from drinking any alcohol and any drinks containing caffeine.

Water will be allowed *ad libitum* except during STT tests. Throughout the study, standardized meals and beverages will be served. Meals will be the same in content and quantity during each confinement period. No food or drinks will be allowed during STT tests.

No cigarettes are to be smoked from midnight ( $\pm 1$  hour) between Visit 2 and Visit 3 until 8 am on the day of Visit 3. On the day of Visit 3, at least 8 hours after last cigarette, cigarette smokers, who want to smoke, will have a cigarette at 8 am $\pm 30$  minutes and then have the STT

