# **5** STUDY POPULATION

This study will enroll 14 study participants: 7 cigarette smokers and 7 never smokers.

The subjects will be divided in two groups:

Group 1 - 7 cigarette smokers

Group 2 - 7 never smokers

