### 4 STUDY POPULATION

#### 4.1 Inclusion criteria

1. Informed of the nature of the study and have agreed to and are able to read, review, and sign the informed consent form (ICF) prior to Screening. The subject must be willing to comply with the study procedures described in the informed consent. The informed consent document will be written in English, therefore the volunteer must have the ability to read and communicate in English.

2. Male subject aged  $\geq$ 25 to  $\leq$ 40 years old.

3. BMI between 18.0 kg/m^2 to 32.0 kg/m^2, inclusive.

4. Judged by the Principal Investigator or designee to be in good health as documented by the medical history, physical examination, vital sign assessments, clinical laboratory assessments, and by general observations.

5. Belong to one of the following two groups:

a. Non-menthol cigarette smoker (meets all of the following criteria at Visit 1 and at Visit 2):

i. A positive urine cotinine test ( $\geq$ 200 ng/mL).

- ii. Smoked at least 20 cigarettes per day for at least the past 5 years.
- iii. eCO levels >10 parts per million (ppm).
- iv. No plans to quit smoking in the next 3 months.
- b. Never smoker (meets all of the following criteria at Visit 1 and at Visit 2):

i. Subject who has smoked less than 100 cigarettes throughout their lifetime and no cigarettes in the past 3 years.

- ii. A negative urine cotinine test (<200 ng/mL).
- iii. eCO levels ≤ 5 ppm.

6. Completed the Screening process within 30 days prior to Visit 2.

7. Availability for the entire study period and willingness to comply with study procedures, including smoking interruptions, as evidenced by a signed ICF and at Visit 2.

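### SAP Appendix 1 derives the never-smoker group at urine cotinine below 50 ng/mL, but controls are enrolled below 200 ng/mL, so a control between the two has no analysis group

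*SAP*

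**What the plan says.** SAP Appendix 1 creates the variable that splits the analysis: "A dichotomous variable (smoker/never smoke) will be calculated". To be a never smoker, a participant must meet every listed criterion at Visit 1 and again at Visit 2, and one of them reads "A negative urine cotinine test (<50 ng/mL".

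SAP Section 4.1 gives the eligibility criterion for the same people as "A negative urine cotinine test (<200 ng/mL". The protocol has the same 200 ng/mL limit in the synopsis, in Section 5.1.1 and in its Appendix B.

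The variable is used throughout. SAP Section 5.5 states: "All descriptive analyses will be performed by smoker and never smoker group". Protocol Section 5 has already fixed each man's group at enrolment, including "Group 2 - 7 never smokers".

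SAP Section 6 is the place for departures from the protocol, introduced by "In this SAP the following assumptions were considered". It lists only which population serves which analysis and does not mention cotinine.

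**The concern.** Eligibility and analysis use different definitions of the control group. A man can be correctly enrolled as a never smoker and then fail the SAP's definition of one. The SAP has no third level and no rule for him.

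Primary objective 2 compares smokers with never smokers, with 7 men per group, and Protocol Section 4.1 says "Study participants will not be replaced after being enrolled". A control lost from the by-group tables is therefore not made good. If someone notices, his group has to be decided without a rule, possibly after the STT results are known. If nobody does, the control group is smaller than planned.

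**Working it through.** **1. The two rules side by side.** Take a control who meets all other never-smoker criteria: fewer than 100 lifetime cigarettes, none in 3 years, exhaled CO at most 5 ppm. The smoker rule needs a positive cotinine test at 200 ng/mL, exhaled CO above 10 ppm and at least 20 cigarettes a day, so he cannot meet it at any cotinine value.

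| Cotinine (ng/mL) | Eligible as never smoker (Protocol 5.1.1, SAP 4.1) | Group under SAP Appendix 1 |
|---|---|---|
| below 50 at both visits | yes | never smoker |
| below 200 at both visits, but 50 or more at one or both | yes | none |
| 200 or above at either visit | no | not enrolled |

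The unclassified band is 50 to below 200 ng/mL.

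**2. Could the difference be innocent?**
- *Text damage.* The equals signs printed before 200 ng/mL and 5 ppm in Appendix 1 are probably lost inequality symbols and are not relied on here. The 50 has an intact sign and is a different number.
- *The amendment.* The protocol revision history lists only the change of upper age limit. SAP 4.1, written from protocol Version 1.0, already has 200 ng/mL.
- *A deliberate tightening.* SAP Section 6 does not record one.

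**3. Where such a man would appear.** SAP 5.3.1 says "All study participants who have at least one evaluable STT test at Visit 3 will be included in FAS population", so he is in the FAS if he has such a test. SAP 5.3.3 puts every enrolled subject in the Safety population. He counts in the Total column of Table A 1. The STT, nicotine and correlation shells (Tables A 4 to A 8) and the vital sign, adverse event and laboratory shells (Tables A 10 to A 15) have only smoker and never-smoker columns, so he has no place in them.

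**4. The plan's own figure.** SAP 5.1 says that 3.75 min is detectable with SD 2.5 min and 7 per group. Power is not stated. Assuming 80% and two-sided 5%:

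n per group = 2 × (1.960 + 0.842)² × (2.5 / 3.75)² = 2 × 7.849 × 0.4444 = 6.98, so 7.

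The figure is reproduced. Normal-approximation power at 7 v 7 is 80.1% (noncentral t: 73.1%).

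**5. Effect of losing controls.** The 95% CI half-width for the control mean is t(0.975, n−1) × SD / √n.

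| SD (min) | n = 7 | n = 6 | Ratio |
|---|---|---|---|
| 2.5 (planned) | 2.4469 × 2.5 / √7 = 2.31 | 2.5706 × 2.5 / √6 = 2.62 | 1.135 |
| 4 (cited for non-smokers, Protocol 2.1) | 2.4469 × 4 / √7 = 3.70 | 2.5706 × 4 / √6 = 4.20 | 1.135 |

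One man is 1/7 = 14.3% of the control group. For scale only, since the study tests no hypothesis, power for 3.75 min at SD 2.5 falls as follows:

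| Group sizes | Normal | Noncentral t |
|---|---|---|
| 7 v 7 | 80.1% | 73.1% |
| 7 v 6 | 76.9% | 69.0% |
| 7 v 5 | 72.6% | 63.7% |

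**The case against.** The case on the other side concerns consequence, not the contradiction.

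- **The band may be empty.** Controls must also have low exhaled CO at both visits and report no tobacco or nicotine product in 3 years. Nothing in the documents suggests that anyone will fall between 50 and 200 ng/mL. This stands, and the numerical effect is conditional on it.
- **The test may be qualitative.** Protocol 7.2.8.5 calls it a screen. If only positive or negative at 200 ng/mL is recorded, the 50 ng/mL rule cannot remove anyone; if the test's cutoff is itself 50, enrolment and derivation agree. This stands as a limit on the likely harm. Protocol 7.2 sends these results to the CRF but does not say whether they are numeric. The SAP names no cotinine listing, although the generic columns of Listing 8 could hold one. A derivation rule that the data may be unable to support is still a reason to correct it.
- **There are safeguards.** Cotinine is measured before the Visit 3 STT tests, the enrolled group is known, changes to SAP definitions must be reported, and the Total column of Table A 1 would expose a mismatch among 14 men. These make silent loss less likely, but they do not say which group the man belongs to.
- **The RNA output.** The Table A 9 shell is arranged by method with a single total column, so it would not be affected. SAP 5.5.4.1, however, says that RNA results are summarised by smoking group. The two disagree; if the text governs, the RNA summaries are exposed too.

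**Conclusion.** The concern holds. The SAP contradicts both the protocol and its own Section 4.1 on the cotinine limit for never smokers. Applied as written, its two-level variable leaves an enrolled control at 50 to below 200 ng/mL unclassified. That part rests on the text alone.

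The size rests on assumptions: at least one control falls in the band, the recorded result can separate 50 from 200 ng/mL, and the rule is programmed literally. Under these, each such man costs one of 7 controls, and the first widens the CI half-width for the control mean by about 13.5%. With none, there is no numerical effect. The point should be fixed because the variable defines the primary comparison and nearly every table, not because a loss is likely.

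**What to change.** In SAP Appendix 1, define the group variable as the group in which the participant was enrolled (Group 1 or Group 2). This is the simpler choice, since it needs no cotinine value and classifies every enrolled man. Alternatively, restore the 200 ng/mL limit so that Appendix 1 agrees with Protocol 5.1.1 and SAP 4.1. Make the change before database lock.

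The cost is SAP wording only; no procedure, sample or data collection changes.

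As separate housekeeping that adds no weight to this point, SAP Sections 1 and 4.1 still follow protocol Version 1.0 (upper age 40) and could be brought to Version 2.0 Amendment 1.0 (upper age 45) in the same edit.
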